Power was computed for an effect size (d) of 0.37, a small-medium effect size to be conservative, based on similar intervention studies in similar facilities comparing groups in terms of high levels of medication adherence and changes in HIV risk behavior.^[4] The computations assume an intraclass correlation (ICC) of 0.500, as we assume conservatively large dependence within participant overtime. Over a 44-month period, 300 participants taking PrEP and enrolled in methadone-maintenance treatment at the APT Foundation (see letter of support) will be recruited and randomly assigned to the two study cells (150 per cell). The criterion for significance (alpha) has been set at 0.05. The test is 2-tailed, which means that an effect in either direction will be interpreted. Given these assumptions (for the effect size, ICC), criteria (for alpha and tails), and plans (for the number of clusters and sample size within cluster), the study will have power of 98.5% to yield a statistically significant result. These same assumptions (for the ICC), and plans (for the number of subjects and time points within subject), the study will allow us to report the effect size (d) with a standard error of approximately 0.089. In order to maintain that power level, we must 288 retain patients at post-intervention, 276 at 3-month follow-up, 258 patients at 6-month follow-up, and 224 patients at 9-month follow-up. Even in the event that only 71% of participants complete the final 9-month follow-up assessment, which would be a conservative estimate based on the previous randomized controlled trials in the same facility among the same patient population, the proposed ample size will still provide sufficient power (94.5%) to detect the expected range of effect sizes.

For EACH Participant Population State Describe the Study Population(s): [Describe the participant population(s) including gender, ethnicity, income, level of education and age range.]

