Participants for trial will be included who are: 1) Are 18 years of age or older; 2) Meet DSM-V criteria for opioid-dependence and are enrolled in methadone maintenance drug treatment at the APT Foundation, Inc.; 3) Were confirmed to be HIV-negative and started on PrEP in the past week; 4) Report unsafe injection drug use practices or unprotected sex within the past 3 months; 5) Have a cell phone; 6) Are able to read and understand the questionnaires, ACASI, and informed consent form; 7) Available for the full duration of the study with no anticipated circumstances impeding participation (e.g., pending charges, jail term). Individuals unable to provide consent and who are actively suicidal, homicidal, or psychotic as assessed by trained research staff under the supervision of the PI who is a licensed clinical psychologist in Connecticut will be excluded.

We plan to recruit 60% men and 40% women (18 years or older) in order to adequately represent the proportion of men and women in the New Haven community. Recruiting 60% men and 40% women should pose no problem given that the men constitute 61% of the APT Foundation MMP (Methadone Maintenance Program), the patient population from which the subjects for the proposed studies will be recruited. However, given that women typically represent 39% of APT MMP population, we plan to increase our efforts to recruit women into the methadone treatment program by posting advertisements at the APT Foundation substance abuse treatment program.

Minorities. We plan to recruit 50% English-speaking minorities; 40% African American and 10% English-speaking Latino/Latina. These target figures are representative of African-Americans and Latino/ Latinas in the community.

Enrollment of UConn Students and/or Employees: [Will UConn students be enrolled? If so, describe if these students include those who any key research personnel teaches, or for whom any key research personnel has responsibility. Will UConn employees be enrolled? If so, describe if these employees

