All opioid-dependent patients enrolled in methadone maintenance treatment will be referred for initial screening. As another precaution, we plan to screen up to 40% more patients than will be needed to meet the proposed sample size. Therefore 420 patients will be screened (i.e., 9 patients per month). In the screening session, conducted by a member of the research staff, determination will be made as to whether the participant meets study inclusion criteria. If so, the participant will be provided with a description of the study. After meeting eligibility criteria, providing informed consent, verifying comprehension of the terms of the study – including being started on PrEP in the past week, and completing the baseline assessment, participants will be randomized to receive, in addition to standard of drug treatment care: (a) 4 weekly group sessions and the 8-week booster session that comprise the CHRP-BB intervention or (b) 4 weekly group sessions and the 8-week booster session that comprise the time-and-attention matched control condition. Participants will be randomized using a computerized “urn” randomization to ensure adequate representation of women and minorities. This technique modifies randomization probabilities based on prior composition of study conditions and reduces the possibility that imbalances between the study groups on variables such as sex and race will occur by chance. Randomization will be stratified by the presence of moderate/severe NCI levels based on the brief inventory of neuro-cognitive impairment (BINI),^[6] to ensure that the proportion of participants at highest risk for poor outcome is equal between intervention arms. The clinicians supervising the MMP will be blind to which intervention the subject is receiving. The standard of care and the intervention conditions will be:

Standard of Drug Treatment Care. Participants in both conditions will receive routine services as part of their enrollment in APT’s methadone maintenance program, which includes daily methadone and case management consisting of a minimum of one hour of monthly contact with a counselor/case manager.

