Intervention Fidelity and Preventing Cross Contamination. We use several procedures to guard against potential threats to internal validity. First, as part of our NIDA-funded work, we have already developed detailed intervention manuals that include detailed session outlines and all other supporting materials needed to conduct the CHRP-BB sessions and the Control condition session have also been manualized. Second, facilitators will complete pre-session checklists and post-session quality assurance forms. Third, we will audiotape all intervention sessions to monitor the content and time allocation of intervention sessions. Using procedures from prior and ongoing intervention trials,^[19, 30, 31, 42] all sessions will be coded for protocol adherence. Fourth, intervention facilitators will meet with the project director and the PI for weekly clinical supervision. Meetings will focus on protocol adherence, resolving issues that arise in sessions, and managing potential “drift”. Study participants will not have contact with each other beyond their participation in routine drug treatment services. In addition, when we become aware of relationship partners enrolling in the study, we will force-randomize them to the same condition in order to avoid cross contamination and violation of group independence. If we find that relationship partners constitute more than 5% of participants, we will include couple status as a factor in our outcome analyses.

Data Analysis: [For all studies, specify the analytic techniques the researcher will use to answer the study questions. Indicate the statistical procedures (e.g. specific descriptive or inferential tests) that will be used and why the procedures are appropriate. For qualitative data, specify the proposed analytic approaches.]

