Hypotheses related to the specific aims: This study is designed to test the primary hypothesis for PWUD prescribed PrEP that the experimental intervention (E=CHRP-BB) is significantly more effective vs. the control condition (S: time-and-attention matched intervention), for the primary outcome of high levels of PrEP adherence (e.g., ≥ 700 fmol/punch or ≥ 4 pills/week)^[25, 26] and secondary outcome of HIV risk reduction behavior. The null hypothesis is that CHRP-BB is not superior to control condition, expressed as $H_0: p_E = p_S$, where p_E is the proportion of participants in CHRP-BB who demonstrate high levels of adherence (e.g., ≥ 700 fmol/punch or ≥ 4 pills/week)^[25, 26] and are free from HIV risk behavior T₃₂post-intervention. Our alternative hypothesis is that the experimental intervention is superior to the control condition, and is expressed as $H_1: p_E > p_S$. Prior to analyzing treatment effects, the degree of pre-test equivalence between experimental and control groups on key variables (e.g., baseline demographics and clinical characteristics) will be evaluated. Baseline data will be evaluated via t-tests and ANOVAs on continuous items when normal or Kruskal-Wallis when we have a non-normal distribution of those items and chi-square tests of categorical items to evaluate pretest equivalence between and within the experimental and control groups. The presence of moderate/severe NCI will be included as a covariate to control for each of the dependent variables. We will use the Bonferroni approach^[43] to correct for alpha inflation with a 0.05 family-wise alpha. Variables in which inequality at baseline is identified will be used as covariates in further analyses to address potential non-equivalence across conditions.^[44] Differential attrition analyses will also be conducted on the data set to assess differential attrition by condition between baseline and subsequent measurements. A series of ANOVAs parametric or non-parametric of Condition (intervention, control) by Retention (retained, not retained) will be conducted on continuous pretest measures^[45]. Any variable influencing differential attrition will be included as a covariate in subsequent analyses.

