Main outcomes analysis plan: The framework for testing the study hypotheses will be to compare differences between the two conditions (CHRP-BB vs. Control) on the main outcome variables. Separate logistic regression models will be used to assess the log odds of having high levels of PrEP adherence and being free from injection or sexual transmission risk behaviors at T₄₄ post-intervention using intervention assignment as a binary coded predictor while controlling for any potential confounders. As an alternative analytical plan for assessing the impact of the two intervention arms on adherence to PrEP, we will use

questionnaires, and collection of urine sample is minimal and adds no risk beyond those normally associated with methadone maintenance treatment. Assessment measures and content of the intervention will involve sensitive and explicit topics related to sexual behavior and substance use. This is necessary given the nature of the intervention and practices that confer risk for HIV infection. However, participants may feel awkward or embarrassed when hearing about or being asked to provide information related to sexual activity. The consent procedure informs participants that sexual behaviors will be explicitly covered in measures and intervention content. Counseling staff will have been trained to observe for signs of subject emotional distress in relation to topic presentation and to employ techniques that prevent, reduce or minimize embarrassment, discomfort, or atypical distress.

Some participants may experience increased anxiety as a result of participating in the intervention. Realistic sensitization and accurate vulnerability self-appraisal are desirable and necessary to motivate behavior change efforts. The investigator is experienced in presenting risk reduction information in ways that link risk to avoidable and modifiable behaviors and risk reduction to the adoption of behavior changes. Counseling staff will observe participants for evidence of becoming overly anxious and will utilize techniques to assure that threat sensitization and vulnerability perceptions are realistic. Research staff will also be knowledgeable of social services that some participants may need, and will assist participants in accessing local resources in areas such as alcohol and other drug abuse treatment, entitlement, and supports for those in or leaving abusive relationships.

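### Baseline tests and an unlisted confounder clause choose the covariates of the main logistic models, and the urn factors are not committed to them; the effect is small and the remedy is mostly wording

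*Combined protocol and SAP*

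**What the plan says.** The covariates of the outcome models are described in several places.

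- **Hypotheses related to the specific aims, baseline tests.** Key variables, given only by example, are compared between arms before treatment effects are analysed. Then: "Variables in which inequality at baseline is identified will be used as covariates in further analyses to address potential non-equivalence across conditions". No threshold is given for a single test.
- **Same section, NCI.** "The presence of moderate/severe NCI will be included as a covariate to control for each of the dependent variables". This is the only covariate with no condition attached.
- **Same section, multiplicity.** Bonferroni is used "to correct for alpha inflation with a 0.05 family-wise alpha". The sentence stands between the baseline tests and the selection rule, but the family of tests is not stated.
- **Same section, attrition.** Variables that influence differential attrition also become covariates. The ANOVAs named for this are on continuous pretest measures.
- **Main outcomes analysis plan.** Separate logistic models at T44 are fitted "using intervention assignment as a binary coded predictor while controlling for any potential confounders". No list follows, and the text breaks off shortly afterwards.
- **Intervention Fidelity and Preventing Cross Contamination.** "If we find that relationship partners constitute more than 5% of participants, we will include couple status as a factor in our outcome analyses".
- **Randomisation paragraph.** Allocation is stratified by NCI and uses an urn that "reduces the possibility that imbalances between the study groups on variables such as sex and race will occur by chance". No visible text puts the urn factors in an outcome model.

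**The concern.** In a randomised trial a baseline difference is a chance event. A test for it says nothing about whether the variable predicts adherence or risk behaviour, which is what makes adjustment useful. The rule also works against the design: factors balanced by the urn will hardly ever look unequal, so it tends to omit the very factors used in allocation.

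The confounder clause adds a second uncertainty. It may mean the variables flagged by the baseline and attrition rules, or it may be an open choice. The adjusted odds ratio is non-collapsible, so it changes with the covariate set even when the arms are balanced. At stake are a fully defined primary model, some power and, on the open reading only, control of Type I error.

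**Working it through.** **Inputs from the documents.** 300 randomised 1:1; two-sided alpha 0.05; d = 0.37; "224 patients at 9-month follow-up"; NCI as stratum; sex and race as example urn factors. **Assumed, because the documents give none:** 10 or 14 independent candidate variables, their prognostic strength, and the dropout patterns.

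**1. The plan's own power.** With five visits and ICC 0.5, the variance factor is (1 + 4 × 0.5)/5 = 0.6. SE = √(2/150 × 0.6) = 0.0894, and power = Φ(0.37/0.0894 − 1.96) = 98.5%. The stated 98.5% and 0.089 reproduce. This figure uses five visits and no covariates, so it neither supports nor refutes the point. The power levels below are for one binary outcome at one visit, so only the differences between columns matter.

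**2. Chance that the rules add a variable.** Take K candidates, with sex and race never flagged.

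| | K = 10 | K = 14 |
|---|---|---|
| Baseline tests at 0.05 each | 1 − 0.95^8 = 33.7% | 1 − 0.95^12 = 46.0% |
| Baseline plus attrition tests at 0.05 | 1 − 0.95^16 = 56.0% | 1 − 0.95^24 = 70.8% |
| Baseline tests, Bonferroni 0.05/K | 1 − 0.995^8 = 3.9% | 1 − (1 − 0.05/14)^12 = 4.2% |
| Both families, Bonferroni 0.05/K | 1 − 0.995^16 = 7.7% | 1 − (1 − 0.05/14)^24 = 8.2% |

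How often the covariate set changes thus depends heavily on a multiplicity sentence whose scope is unstated.

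**3. The mechanical rule, and adding the urn factors.** Simulation: 8,000 trials per setting, urn on sex and race within NCI, 224 analysed, K = 14. The treatment log-odds ratio is 0.37 × π/√3 = 0.671 (OR 1.96).

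| Assumed prognostic OR | Power: NCI only | Power: baseline-test rule | Power: NCI + sex + race | Null rejection: rule | Null rejection: NCI + sex + race |
|---|---|---|---|---|---|
| 1 | 71.0% | 70.4% | 71.0% | 5.3% | 5.3% |
| 1.5 | 68.9% | 68.6% | 69.4% | 4.9% | 4.9% |
| 2 | 64.9% | 64.7% | 67.0% | 4.9% | 5.6% |
| 3 | 58.3% | 58.0% | 63.3% | 4.3% | 5.5% |

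Monte Carlo SE near 5% is √(0.05 × 0.95/8000) = 0.24 points. Against NCI only, the rule costs 0.6, 0.3, 0.2 and 0.3 points. Adding sex and race gains 0.0, 0.5, 2.1 and 5.0 points (differences of the rounded entries). Sex or race was flagged in 0.0% of trials.

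A second simulation (212 analysed, 10 further variables, 4,000 trials) agrees. Under the null the rule rejected in 3.5% to 4.5% of trials. Adding sex and race gained 61.4 − 58.3 = 3.1 points at OR 2 and 49.3 − 44.2 = 5.1 at OR 3.

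**4. Open choice, assumed worst case.** NCI is forced in, every subset of five candidates (32 models) is fitted, and the smallest p-value is reported. Simulations of at least 3,000 null trials per setting, n = 224, gave these ranges across runs:

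| Candidate OR per SD | Null rejection |
|---|---|
| 1 | 6.0–6.8% |
| 1.3 | 8.6–9.2% |
| 1.5 | 9.5–11.3% |
| 2 | 13.6–14.4% |

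NCI-only models gave 4.1–6.2%. With two candidates (four models) the figures were 5.4–9.3%. Across the 32 models the highest odds ratio exceeded the lowest by a median factor of 1.06 to 1.38.

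**5. The attrition rule.** 4,000 null trials per setting; retention OR 1.5 per SD in opposite directions by arm. For outcome ORs of 1.3, 1.5 and 2, a model without the dropout variable rejected in 5.7%, 6.1% and 7.5% of trials. With the plan's attrition rule at 0.05 the figure was 5.1–5.4%. At a retention OR of 1.2 there was no material difference.

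**6. Baseline risk as a covariate.** Entry requires that participants "Report unsafe injection drug use practices or unprotected sex within the past 3 months", so almost nobody is free from risk at T0. At an assumed 2%, that is 224 × 0.02 = about 4.5 people. At a prognostic OR of 2 per SD, power was 62.8% with no T0 covariate, 63.4% with the binary status and 66.7% with a frequency measure.

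**The case against.** A reader might infer that baseline testing inflates Type I error. It does not: null rejection under the rule was 3.5% to 5.3%.

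A reader might also infer that the analyst may search models for the best result. The documents do not describe that. The confounder clause is naturally read as pointing back to the two selection rules, and the baseline evaluation is placed before treatment effects are analysed. On that reading the covariates follow from baseline and retention data, not from outcomes. This stands, and the 14% figure is only a bound under an assumption. What remains open is that the candidates are given only by example, no threshold is stated, and the clause is not tied to the rules in words.

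The Bonferroni sentence may well govern the baseline tests, given where it stands. If so, additions are rare (3.9–4.2%), but its scope should still be stated.

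The gain from the urn factors is close to zero unless they are clearly prognostic, and it comes from adding them rather than from ending test-based selection. Both points stand. Nor does the plan bar sex or race from the model: they could enter as confounders, and the attrition rule does not expressly exclude them. They are simply not assured.

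Finally, unseen text could contain a covariate list. If it does, a cross-reference would settle much of the point.

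**Conclusion.** The point holds as a limited one. In the visible text the main models have one unconditional covariate, a selection rule that ignores prognostic value and passes over the allocation factors, and a confounder clause with no list.

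Applied mechanically, the rule costs under 1 point of power and does not inflate Type I error. Naming sex and race gains about 0 to 5 points for assumed odds ratios of 1 to 3. Rejection rates of about 6% to 14% arise only if covariates are picked after seeing results, which the text does not say is intended.

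The tempting further step, removing all data-driven covariates from the primary model, is not supported. The attrition rule protects against arm-specific dropout, and removing it could do harm (up to 7.5% null rejection in the scenario above). The case for change is that analysing by the factors used to allocate is nearly free. The simulated sizes rest on assumed candidate numbers, independence and prognostic strengths; the direction is more reliable than any single figure.

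**What to change.** - **Hypotheses section.** Delete the rule that baseline inequality selects covariates. Report baseline comparisons descriptively, and move models that add imbalanced variables to sensitivity analyses.
- **Hypotheses section and Main outcomes analysis plan.** Define the primary model as condition, NCI stratum and the factors actually used in the urn, each listed, plus couple status under the existing 5% rule. Replace the confounder clause with that list.
- **Attrition.** Keep the attrition rule in the primary model. Name its candidate variables and threshold before outcomes are analysed.
- **Multiplicity.** State which tests the Bonferroni correction covers.
- **Optional, risk-behaviour outcome only.** Add a named T0 risk-frequency measure, not the nearly constant binary status.

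The cost is wording plus a few decisions: the urn list, the attrition candidates and threshold, the Bonferroni family and, if used, the T0 measure. No new data are needed, since NCI and the urn factors are known at randomisation and HIV risk behaviour is collected at all assessments. Couple status and attrition variables would still depend on enrolment and retention data, but under stated rules. The downside is that the primary model no longer adapts to chance baseline imbalance, which the sensitivity analyses cover.

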PrEP adherence. This outcome will be assessed using a biomedical and behavioral approach: (1) Biomedical - For the biomedical assessment, which will occur immediately post-intervention and at the T₂₀, T₃₂, and T₄₄ post-intervention follow-ups, we will quantify tenofovir-diphosphate (TFV-DP) and emtricitabine-triphosphate (FTC-TP) in RBC, measured with dried blood spots (DBS; see [name] letter of support) as a well validated adherence measure.^[23-26] This test assesses cumulative adherence because TFV-DP in RBC exhibits a 17-day half-life and 25-fold accumulation. This enables assessment of cumulative TFV exposure (adherence) over the preceding 1-2 months for TFV-based regimens. FTC-TP has a shorter half-life (~35 hours) such that detection correlates with recent dosing, similar to detection of tenofovir in plasma. One or two drops of blood will be collected for DBS by using a standard finger-stick with a lancet (DBS-FS) by trained research staff and dried blood spots will be prepared, which will be stored at -20° C within 24 hour of collection. Specimens will be shipped on dry ice to the Colorado Antiviral Pharmacology Laboratory located in Aurora, Colorado (UC Denver-Skaggs School of Pharmacy and Pharmaceutical Sciences, [name]). TFV-DP and FTC-TP will be quantified with a validated liquid chromatography tandem mass spectrometry method.^[25, 27] (2) Self-reported PrEP adherence will be included in our ACASI battery (see above description) using a visual analogue scale (VAS).^[28] The VAS is empirically validated, consistently under-reports adherence, but effectively measures a "difference" in adherence that changes in response to an intervention. (3) In addition, as in our prior studies,^[18, 29] we will use pharmacy refill data as an additional objective data source. As used in current studies, a release of information to obtain pharmacy data from both Medicaid and individual pharmacies will be deployed. Thus, we will allow us to triangulate PrEP adherence so that we can assess the correlation (r) between biomedical and self-report measures as well as compare with pharmacy refill data.

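### The named main analysis is a single-visit logistic regression at T44 that makes no use of the T8, T20 and T32 drug levels, and it is not the analysis for which power was stated

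*Combined protocol and SAP*

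**What the plan says.** The main outcomes analysis plan (under Data Analysis) names the model: "Separate logistic regression models will be used to assess the log odds of having high levels of PrEP adherence" and, separately, of being free of transmission risk behaviour, both at T44. It then announces an alternative analysis for adherence, but the available text breaks off before describing it.

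The PrEP adherence section schedules the drug levels: "For the biomedical assessment, which will occur immediately post-intervention and at the" T20, T32 and T44 follow-ups. That is four post-baseline levels per person and none at baseline. Pharmacy refill data are also planned.

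The sample-size justification says "Power was computed for an effect size (d) of 0.37". It adds "The computations assume an intraclass correlation (ICC) of 0.500", described as dependence within a participant over time. Participants are "randomly assigned to the two study cells (150 per cell"), and "The criterion for significance (alpha) has been set at 0.05", two-tailed. Stated power is 98.5%, with a standard error of 0.089 for d. The retention needed to keep that power includes "258 patients at 6-month follow-up, and 224 patients at 9-month follow-up". If only 71% complete the last visit, stated power is 94.5%.

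On attrition, the section on hypotheses related to the specific aims tests pretest measures by condition and retention, and says: "Any variable influencing differential attrition will be included as a covariate in subsequent analyses". The same section places the hypothesis at T32, not T44.

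**The concern.** A logistic model with one T44 outcome per person takes nothing from earlier visits. Unless another rule is given, someone without a T44 sample contributes nothing to the adherence comparison, even with three earlier drug levels on file.

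This matters because dropout may be related to adherence. The Risk/Benefit Analysis itself describes the participants as being at high risk of dropout. If people who stop PrEP are also those who miss T44, the observed proportion is too high in both arms, and the comparison is biased if the process differs by arm. Adjusting for pretest variables does not reach this mechanism: no drug level is scheduled before T8, so there is no baseline level to adjust for.

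A second problem follows. The power statement assumes repeated measures within a person, which the named model does not use. The stated power therefore does not describe the test that would be run.

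**Working it through.** **Inputs from the documents.** d = 0.37; ICC = 0.5; 300 randomised 1:1; two-sided alpha 0.05; retained 288, 276, 258 and 224 at T8, T20, T32 and T44; conservative T44 case 71%, i.e. 0.71 × 300 = 213.

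**Missing at T44.** 300 − 224 = 76 (25.3%). 300 − 213 = 87 (29.0%). At T32, 300 − 258 = 42 (14.0%).

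**Reproducing the stated power.** For the average of m visits, SE = √{[(1 + (m − 1) × ICC)/m] × 4/N}, and power ≈ Φ(d/SE − 1.96).

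| Visits m | N | SE | Power |
|---|---|---|---|
| 5 | 300 | 0.0894 | 98.5% |
| 4 | 300 | 0.0913 | 98.2% |
| 1 | 300 | 0.1155 | 89.3% |

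Of one to five visits, only five matches both stated figures. With m = 5, power is 94.7% at N = 224 and 93.7% at N = 213, close to the stated 94.5%. Five visits include baseline, where no drug level is scheduled.

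**Power of the named comparison.** With m = 1, SE = √(4/N):
- N = 224: SE 0.1336, power 79.1%.
- N = 213: SE 0.1370, power 77.0%.
- At T32 instead, N = 258: power about 84%.

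These treat d as a difference on a continuous scale. The outcome is binary. As an assumption, converting d to an odds ratio, exp(0.37 × π/√3) = 1.96, with a control rate of 20% to 60%, gives 59–70% at 224 and 57–68% at 213.

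**Precision gain for the same T44 contrast.** Generalised least squares on the four drug-level visits, assuming monotone dropout and exchangeable correlation 0.5:
- N = 224: SE 0.128, power 82.2% (was 79.1%).
- N = 213: SE 0.131, power 80.9% (was 77.0%).

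Variance falls by 8–9%. If 0.5 is instead the correlation on an underlying normal scale, it is about 0.33 after dichotomising, and power is 80.7% and 79.0%. The gain is thus about 2 to 4 points.

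**Possible attrition bias (all rates assumed).** No true effect; 45% highly adherent in each arm; 20% among those lost. With retention r, the proportion among completers is (0.45 − (1 − r) × 0.20)/r, and n = 150r per arm.

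| Retention, arm 1 vs arm 2 | Completers' proportions | Spurious difference | False-positive rate |
|---|---|---|---|
| 67% vs 75% | 57.3% vs 53.3% | 4.0 points | 9% |
| 64% vs 78% | 59.1% vs 52.1% | 7.0 points | 18% |
| 71% vs 71% | 55.2% vs 55.2% | 0 | 5% |

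In this model equal retention biases the level of adherence (55% instead of 45%) but not the comparison.

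**What using earlier levels would repair.** In a simulation of the 64% vs 78% case, essentially all the bias goes when dropout depends on observed earlier levels. When dropout depends on T44 adherence itself, 5.7 to 6.0 of the 7.0 points remain in simulations with an underlying correlation of 0.5.

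**The case against.** The strongest objection is that the text is incomplete. The description of the alternative adherence analysis is missing, and it could be longitudinal or include a missing-data rule. That stands as a limit: a reader might infer that the plan drops everyone without a T44 sample, but the documents do not say so. Leaving them out is only the default behaviour of a logistic model. Even so, the alternative is labelled as such, and the main model is stated.

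A reader might also infer that the trial as a whole ignores the earlier drug levels. It does not: the design description commits to examining the trajectory of adherence over time. Only the named main model leaves them out.

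Nor do the documents predict a loss of 25–29%. The 224 is a retention requirement and the 71% a conservative case. If the primary time point is T32, the planned loss is 14%.

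On size, the objection is largely right. The precision gain is modest. The bias figures rest on assumed rates, and the between-arm bias in that illustration needs unequal retention, which no section forecasts; the control condition is matched for time and attention. Earlier levels are also not always available: under monotone dropout, 42 of the 76 missing at T44 also lack T32, and 12 have no drug level at all (300 − 288).

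Finally, a mixed logistic model estimates a participant-specific odds ratio, whereas the hypothesis concerns proportions. This is valid, and the fix allows for it.

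**Conclusion.** The point holds in a limited form. The named main analysis uses one of four scheduled drug levels, and the readable remedy for attrition cannot address dropout related to adherence after baseline. The stated power belongs to a different analysis: 98.5% and 94.5% are claimed, against about 79% (224) and 77% (213) for the T44 comparison at d = 0.37 on a continuous scale.

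The case for change rests mainly on bias, not precision. It is strong if dropout is related to earlier observed levels and weak if it is driven by unobserved adherence at the final visit. The documents do not show which applies, so the bias is a risk of unknown size, not a demonstrated error. A reader might infer that a repeated-measures model would restore the stated power. For the same T44 contrast it would not, since power stays near 79–82%. Averaging over the four visits gives 97.4%, but that answers a different question and needs a constant effect, whereas the design description anticipates decay or emergence.

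The change should be made, with medium confidence, because it is cheap and uses data already planned.

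**What to change.** 1. Reconcile T32 (hypotheses) and T44 (main outcomes analysis plan) as the primary time point.
2. Make the primary analysis one that uses all post-baseline drug levels in all randomised participants, with arm, visit, arm-by-visit and the neurocognitive-impairment stratum. Either multiple imputation from earlier TFV-DP levels and pharmacy refill data, or a mixed logistic model with marginal standardisation, would serve.
3. Report the contrast at the chosen time point as a population-level difference in proportions or marginal odds ratio, so that it matches the hypothesis.
4. Add a sensitivity analysis that counts a missing sample as not highly adherent, because the primary model would assume data missing at random.
5. Keep the single-visit logistic regression as supportive.
6. Restate the power for the contrast actually tested, on the binary scale and at the alpha that applies after the planned Bonferroni correction.

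If the alternative adherence analysis is already longitudinal, much of this amounts to promoting it. The cost is plan wording, modest programming and reliance on a missing-at-random assumption. No new visits or samples are needed.
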